Appendix 2: Markedly Abnormal Laboratory Parameter Values

Chemistry

Laboratory Value (SI Unit)	Lower Limit of Normal (LLN) Range	Upper Limit of Normal (ULN) Range	DNP Recommended Markedly Abnormal: Low	DNP Recommended Markedly Abnormal: High
Alanine Amino Transferase – ALT (SGPT)(U/L)	1	30	NA	$\geq 3 \times \text{ULN}$, OR $\geq 5 \times \text{ULN}$, OR $\geq 10 \times \text{ULN}$
Aspartate Amino Transferase - AST (SGOT)(U/L)	0	35	NA	$\geq 3 \times \text{ULN}$, OR $\geq 5 \times \text{ULN}$, OR $\geq 10 \times \text{ULN}$
Albumin(g/L)	<5 years: 29 ≥ 5 years: 31	<5 years: 58 ≥ 5 years: 54	<5 years: ≤ 20 ≥ 5 years: ≤ 25	<5 years: ≥ 65 ≥ 5 years: ≥ 60
Alkaline Phosphatase(U/L)	Females: 2-10 years: 100 11-17 years: 100 ≥ 18 years: 30 Males: 2-10 years: 100 11-17 years: 100 ≥ 18 years: 30	Females: 2-10 years: 320 11-17 years: 320 ≥ 18 years: 120 Males: 2-10 years: 320 11-17 years: 390 ≥ 18 years: 120	NA	$> 3 \times \text{ULN}$
Ammonia(umol/L)	≤ 18 years: 21 ≥ 18 years: 0	≤ 18 years: 50 ≥ 18 years: 35.7	NA	$\geq 1.5 \times \text{ULN}$
Bicarbonate/			Value < 17, OR	

Laboratory Value (SI Unit)	Lower Limit of Normal (LLN) Range	Upper Limit of Normal (ULN) Range	DNP Recommended Markedly Abnormal: Low	DNP Recommended Markedly Abnormal: High
Carbon Dioxide (CO ₂) (mmol/L)	20	26	(Value < 17 and decrease from pre-treatment baseline > 5 when pre-treatment baseline ≥ 20)	≥ 31
Bilirubin – Total (umol/L)	1.7	20.5	NA	≥ 41
Blood Urea Nitrogen (BUN) (mmol/L)	2.5	7.9	NA	≥ 16
Calcium (mmol/L)	2	2.6	≤ 1.7	≥ 3
Chloride (mmol/L)	96	109	NA	≥ 112 OR ≥ 115
Total Cholesterol (mmol/L)	≤ 18 years: 0 ≥ 18 years: 0	≤ 18 years: 5.18 ≥ 18 years: 6.2	NA	≥ 1.2 X ULN
Creatinine (umol/L)	2-12 years: 27 13-17 years: 44 ≥ 18 years: Males 53 Females	2-12 years: 62 13-17 years: 88 ≥ 18 years: Males 115 Females	NA	≥ 1.6 X ULN

	44	106		
Creatine Kinase (CK) (U/L) – collected only in TOPMAT-MIG-3006	Females:	Females:	NA	≥ 1.6 X ULN
	0-3 years:	0-3 years:		
	18	134		
	4-6 years:	4-6 years:		
	18	147		
	7-9 years:	8-9 years:		
	18	295		
	10-12 years:	10-12 years:		
	18	184		
	13-15 years:	13-15 years:		
	18	187		
	16-17 years:	16-17 years:		
	18	169		
	≥18 years:	≥18 years:		
	18	169		
	Males:	Males:		
	0-3 years:	0-3 years:		
	18	163		
	4-6 years:	4-6 years:		
	18	158		
7-9 years:	7-9 years:			
18	354			
10-12 years:	10-12 years:			
18	363			
13-15 years:	13-15 years:			
18	363			
16-17 years:	16-17 years:			
18	408			
≥18 years:	≥18 years:			
18	198			
G-Glutamyl Transferase (GGT)	<18 years:	<18 years:	NA	≥ 3 X ULN
	0	23		
Glucose (mmol/L)	<16 years:	<16 years:	≤ 0.8 X LLN (e.g., ≤ 2.6 for ≤ 16 years and ≤ 3.1 for > 16 years)	≥ 1.2 X ULN (e.g., ≥ 7.0 for ≤ 16 years and ≥ 7.7 for ≥ 16 years)
	3.3	5.8		
	≥16 years:	≥16 years:		
	3.9	6.4		

Phosphorus Inorg. (mmol/L)	<18 years: 1.03 ≥18 years: 0.87	<18 years: 2.10 ≥18 years: 1.45	< 0.8 X LLN	> 1.4 X ULN
Lactate Dehydrogenase (U/L)	<18 years: 150 ≥18 years: 0	<18 years: 300 ≥18 years: 220	NA	> 2 X ULN
Potassium (mmol/L)	3.5	5	≤3.0	≥ 5.7
Sodium(mmol/L)	135	148	≤127	≥158
Total Protein(g/L)	<6 years: 49 ≥6 years: 60	<6 years: 81 ≥6 years: 80	≤0.7 X LLN	≥1.25 X ULN
Triglycerides (mmol/L)	Females: 0-5 years: 0.3616 6-11 years: 0.3955 12-15 years: 0.4633 16-19 years: 0.452 Males: 0-5 years: 0.339 6-11 years: 0.3503 12-15 years: 0.4068 16-19 years: 0.452	Females: 0-5 years: 1.1187 6-11 years: 1.2882 12-15 years: 1.5594 16-19 years: 1.4464 Males: 0-5 years: 0.9718 6-11 years: 1.2204 12-15 years: 1.5594 16-19 years: 1.8419	NA	> 1.6 X ULN
Uric Acid (umol/L)	140	380	≤ 80	≥ 570

Magnesium	Females: 1-3 years:	Females: 1-3 years:	<0.5	>2
	0.7	0.98		
	4-6 years:	4-6 years:		
	0.7	0.90		
	7-12 years:	7-12 years:		
	0.7	0.90		
	13-15 years:	13-15 years:		
	0.66	0.94		
	16-18 years:	16-18 years:		
	0.62	0.90		
	Males:	Males:		
	1-3 years:	1-3 years:		
	0.7	0.98		
	4-6 years:	4-6 years:		
	0.7	0.98		
	7-12 years:	7-12 years:		
	0.7	0.90		
	13-15 years:	13-15 years:		
	0.66	0.94		
	16-18 years:	16-18 years:		
	0.62	0.90		

In addition, the MAL low and high for additional parameters will be as follows:

Parameter	MAL low	MAL high
25 Vitamin D (ng/ml)	<20	>55
1, 25 D (pg/ml)	<15	>90
IGF-1 (nmol/L)	2-8: <6	>50
	9-10: <8	>65
	11-12: <15	>100
	13-16: <20	>140
PTH (pg/mL)	2-7: <40	>350
	8-10: <50	>490
	11-12: <70	>750
	13-16: <100	>1100

The conversion factors for 25 Vitamin D, 1, 25 Vitamin D and PTH are listed below.

Parameter	Units	Conversion factor
25 Vitamin D	nmol/L to ng/mL	0.4
1, 25 Vitamin D	Pmol/L to pg/ml	1.355
PTH	Pmol/L to pg/mL	9.434

Hematology

Laboratory Value (SI Unit)	Lower Limit of Normal (LLN) Range	Upper Limit of Normal (ULN) Range	DNP Recommended Markedly Abnormal: Low	DNP Recommended Markedly Abnormal: High
Hemoglobin (g/L)	Females: 1-4 years: 109 5-10 years: 119 11-17 years: 119 ≥18 years: 119 Males: 1-4 years: 109 5-10 years: 119 11-17 years: 127 ≥18 years: 132	Females: 1-4 years: 150 5-10 years: 150 11-17 years: 150 ≥18 years: 155 Males: 1-4 years: 150 5-10 years: 150 11-17 years: 170 ≥18 years: 177	≤ 90	≥ 180

Hematocrit (proportion of 1.0)	Females: 1-4 years: 0.31 5-10 years: 0.35 11-17 years: 0.34 ≥18 years: 0.35 Males: 1-4 years: 0.31 5-10 years: 0.35 11-17 years: 0.37 ≥18 years: 0.40	Females: 1-4 years: 0.44 5-10 years: 0.44 11-17 years: 0.44 ≥18 years: 0.47 Males: 1-4 years: 0.44 5-10 years: 0.44 11-17 years: 0.48 ≥18 years: 0.52	≤0.85 X LLN	≥1.15 X ULN
RBC – Total (10E12/L)	Females: 1-4 years: 3.8 5-10 years: 4.1 11-17 years: 3.9 ≥18 years: 4.2 Males: 1-4 years: 3.8 5-10 years: 4.3 11-17 years: 4.3 ≥18 years: 4.5	Females: 1-4 years: 5.2 5-10 years: 5.2 11-17 years: 5.1 ≥18 years: 5.4 Males: 1-4 years: 5.5 5-10 years: 5.2 11-17 years: 5.6 ≥18 years: 6.2	≤0.85 X LLN	≥1.15 X ULN

WBC – Total (10E9/L)	2-5 years: 5 6-17 years: 4.5 ≥18 years: 4.5	2-5 years: 15.5 6-17 years: 13.5 ≥18 years: 11	< 0.85 X LLN	> 1.15 X ULN
Neutrophils– WBCDifferential Count(Proportion of 1)	0.38	0.80	≤ 0.15	≥ 0.90
Lymphocytes– WBCDifferential Count(Proportion of 1)	0.15	0.40	≤ 0.10	≥ 0.60
Monocytes– WBCDifferential Count(Proportion of 1)	0	0.13	NA	≥ 0.20
Eosinophils– WBCDifferential Count(Proportion of 1)	0	0.08	NA	≥ 0.10
Basophils – WBC Differential Count (Proportion of 1)	0	0.02	NA	≥ 0.06
Platelet Count (x10E9/L)	150	350	≤ 0.75 X LLN	≥ 1.3 X ULN

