13. Subject has clinically relevant abnormalities noted on renal ultrasound or DEXA scans. Subjects with baseline BMD Z-scores ≤ -2 , for either posterior-anterior lumbar spine (L1-L4) or total body less head, will not be enrolled.
14. Subject has congenital glaucoma or known ocular deficits, or is receiving any ocular medications except lubricating eye drops or topical antibiotics.
15. Subject has a known history of central hyperthermia, dysautonomia, or other disturbances of autonomic function.
16. Subject has a known history of inborn errors of metabolism, mitochondrial dysfunction, or prior evidence of hyperammonemia.

-
17. Subject has any clinically significant abnormality in laboratory tests at screening, including but not limited to:
 - WBC count $<3,000/\mu\text{L}$ or absolute neutrophil count $<1,000/\mu\text{L}$ in the last 6 months
 - Aspartate aminotransferase (AST), alanine aminotransferase (ALT), or gamma-glutamyltransferase (GGT) ≥ 3 times the ULN
 - Total bilirubin ≥ 1.5 mg/dL or conjugated bilirubin $\geq 20\%$ of total
 - Venous ammonia ≥ 2 times the ULN
 - 25-hydroxy-vitamin D (level for clinically significant vitamin D deficiency is <12.0 ng/mL, conventional units [<30 nmol/L, SI units])^{19,42}
 - Parathyroid hormone (normal reference range is 14.0 to 72.0 pg/mL)
 - 1,25-dihydroxy-vitamin D, as determined by the age-dependent reference ranges (see lab manual)
 - Insulin-like growth factor 1 (IGF-1), as determined by the age-dependent reference ranges (see lab manual)
 18. Subject has a bicarbonate level <20 mEq/L, has a diagnosis of metabolic acidosis, or is on alkali therapy.
 19. Subject has refractory epilepsy and requires adjunctive AED therapy or is receiving >1 concurrent AED (including benzodiazepines, regardless of the reason for prescription).
 20. Subject is being treated with furosemide, hydrochlorothiazide, vigabatrin, vitamin B₆ therapy for epilepsy, monoamine oxidase (A or B) inhibitors, felbamate, zonisamide, or any other medication that is a potent carbonic anhydrase inhibitor (eg, acetazolamide). Past treatment with furosemide for more than 2 weeks must be discussed with the sponsor and the discussion documented.

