At the discretion of the investigator, one or more of these laboratory parameters may be evaluated at the local laboratory to reduce the duration of the screening phase. In such instances, the local laboratory instructions should be followed and local reference ranges should be applied. The local laboratory results would be used for decision regarding randomization. The central laboratory evaluation results will be used for study data analysis. The additional use of a local laboratory might lead to an additional amount of blood volume to be drawn from the subject at screening.
- Urinalysis will be performed by the central laboratory, and will include dipstick and sediment as noted below. If dipstick result is abnormal, flow cytometry will be used to measure sediment. In case of discordance between the dipstick results and the flow cytometric results, the sediment will be examined microscopically.

Dipstick

-specific gravity
-pH
-glucose
-protein
-blood
-ketones
-nitrite

Sediment

-RBCs
-WBCs
-epithelial cells
-crystals
-casts
-bacteria

- Urine Pregnancy Testing (for girls of childbearing potential only) to be obtained at all visits after screening during the open-label treatment phase. If a girl starts menstruating and becomes of childbearing potential during the study, urine pregnancy tests should be obtained at all subsequent visits during the open-label treatment phase.
- 24-Hour Urine Collection: A 24-hour urine collection will be analyzed for pH, calcium, citrate, phosphorus, and creatinine levels. Collection instructions and storage conditions will be specified in the laboratory manual. A 14-day window on either side of the scheduled Month 6 visit will be allowed for 24-hour urine collection. The collection at Month 12 should be completed before the Month-12 visit as this evaluation should be obtained while the subject is still receiving study-drug therapy.

Additional use of local laboratories is allowed in cases where safety follow-up is time-critical and the central laboratory results are not expected before the need to take actions for safety reasons.

After consultation with the medical monitor, investigators may obtain additional laboratory assessments and/or advice from local medical consultants in the event of any clinically important safety concern.

Bone Age Radiograph

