5	Month 3	76 to 135	90
6	Month 6	136 to 225	180
7	Month 9	226 to 315	270
8	Month 12	>=316	360

^a The randomization day is Day 1.

The analysis windows for DEXA is given in [Table 8](#).

Table 8: Definition of windows for DEXA:

Scheduled Visit Number	Time Interval (label on output)	Time Interval (Day) ^a	Target Time Point
1, 2	Baseline	-35 to 30	1
6	Month 6	31 to 270	180
8	Month 12	>=271	360

^a The randomization day is Day 1.

The analysis windows for Pharmacokinetics is given in [Table 9](#).

Table 9: Definition of windows for Pharmacokinetics

Scheduled Visit Number	Time Interval (label on output)	Time Interval (Day) ^a	Target Time Point
3	Month 1	2 to 45	30
5	Month 3	46 to 135	90
6	Month 6	136 to 270	180
8	Month 12	>=271	360

^a: The randomization day is Day 1

Baseline is defined as the last non-missing observation (including an unscheduled visit) prior to or equal to Day 1 (except for DEXA and Bone age, where baseline includes up to 30 days and 180 days post-baseline, respectively).

For post baseline observations, if more than one visit (including an unscheduled visit) occurs in the same time window, the visit nearest to the target day will be used in the analysis. In the case of an equal distance in time, the latest visit will be used.

Data that are not used in the analysis due to multiple observations or being excluded from the above defined time intervals will be displayed in the data listing.

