7.10. Clinical Laboratory Tests

Figures of the mean change from screening (+/- Standard Error) values in continuous hematology, urinalysis and serum chemistry laboratory parameters will be presented by visit. The observed and change from baseline values of lab parameters will also be summarized by visit. For calculation, the signs “<” or “>” will be removed and resulting numerical value will be used. The reference ranges for labs from the SAP will be used, not the reference ranges provided from the Covance.

The shift table of pre- vs. post-treatment with classes for below, within, and above normal ranges will be presented.

The number and percentage of subjects with markedly abnormal (low, high) laboratory hematology, urinalysis/24-hour urine and serum chemistry parameters during the study (from treatment start to 30 days after last dose or the end of treatment visit date, whichever is later) that were not present at baseline will be provided. [Appendix 2](#) presents the markedly abnormal criteria. The conversion factors for 25 Vitamin D, 1, 25 Vitamin D and PTH are also listed.

The laboratory data will be listed. The subjects with any laboratory results outside the reference ranges and the subjects with any markedly abnormal laboratory results will be listed.

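### The new-onset count for low 25-hydroxy-vitamin D uses a 20 ng/mL flag, so a child entering at 12 to <20 ng/mL cannot be counted on falling below the protocol's 12 ng/mL deficiency limit

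*SAP*

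**What the plan says.** The supplementary table at the end of the chemistry part of SAP Appendix 2 has a row "25 Vitamin D (ng/ml" with a low limit of <20 and a high limit of >55. The same appendix converts nmol/L to ng/mL with a factor of 0.4.

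SAP 7.10 tabulates the number and percentage of subjects with markedly abnormal values "that were not present at baseline will be provided". It separately states that "the subjects with any markedly abnormal laboratory results will be listed", and that listing is not limited to new abnormalities.

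SAP 3.1 fixes the reference value: "Baseline is defined as the last non-missing observation (including an unscheduled visit) prior to or equal to Day 1". Both schedules place this assay at screening, Month 6 and Month 12/early withdrawal, so the baseline is normally the screening sample.

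Protocol 4.2, exclusion 17, states for 25-hydroxy-vitamin D: "level for clinically significant vitamin D deficiency is <12.0 ng/mL, conventional units", with 30 nmol/L as the SI equivalent. When a site also uses a local assay at screening, Protocol 9.3 says "The local laboratory results would be used for decision regarding randomization" and "The central laboratory evaluation results will be used for study data analysis".

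Protocol 11.4 includes change from baseline in this marker among its key safety endpoints. SAP 7.5 summarizes observed values and changes by visit.

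**The concern.** Two cut-offs for the same analyte sit in the two documents, and the SAP's baseline condition makes the difference matter. A child who enters between them is flagged before treatment starts and so cannot enter the new-low count, however far the value later falls. SAP section 3 generally takes the analysis population as denominator, so this child still counts there. A child with adequate baseline stores who drifts just under 20 ng/mL does enter the count.

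The table that a reader would consult for treatment-emergent low vitamin D by arm therefore cannot show new deficiency, as the protocol defines it, among the children who start closest to it. In a study whose primary objective includes bone mineralization, a difference between arms in that event may go unseen in this table.

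**Working it through.** **1. Is the gap a unit slip?** Apply the SAP factor of 0.4.

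- Protocol limit: 30 nmol/L × 0.4 = 12.0 ng/mL. This reproduces the protocol's own pair of figures exactly.
- SAP flag: 20 ng/mL ÷ 0.4 = 50 nmol/L.

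The two limits are different levels on a common scale.

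**2. Who can be counted?** Let B be the central baseline and P a later central value, in ng/mL. A child enters the new-low count when B ≥ 20 and P < 20.

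| Baseline | Later value | Below protocol limit of 12? | In new-low count? |
|---|---|---|---|
| 15 | 10 | yes | no (flagged at baseline) |
| 21 | 19 | no | yes |
| 21 | 11 | yes | yes |

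The blocked band is 12 ≤ B < 20, which is 20 − 12 = 8 ng/mL wide (30 to <50 nmol/L). A countable child must fall by more than 8 ng/mL to be deficient on the protocol's limit. Any counted value from 12 to <20 is not deficient on that limit.

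**3. Do other tables in SAP 7.10 fill the gap?** The shift table uses classes below, within and above normal, with ranges taken from the SAP. Appendix 2 gives no normal range for 25-hydroxy-vitamin D, only the markedly abnormal limits. As written, the shift table has no class boundary at 12 for this analyte.

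**4. How large could the effect be?** The documents give no mean, SD or correlation, so this step rests on assumptions:

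- baseline normal, mean 22, 26, 30 or 35 and SD 7 or 10 ng/mL, truncated at 12;
- one later value, with normal change independent of baseline, mean 0, −3, −6 or −10 and SD 4, 7 or 10 ng/mL.

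That is 4 × 2 × 4 × 3 = 96 scenarios.

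| Quantity | Range over 96 scenarios |
|---|---|
| Children blocked (12 ≤ B < 20) | 1.5% to 34% |
| Counted cases with P ≥ 12 | 45% to 98% |
| Later values <12 missed because B < 20 | 7% to 97% |

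One mid-range scenario (mean 26, SD 7, change mean −3, SD 7) gives about 18%, 78% and 59% respectively. The share of counted cases at or above 12 is below one half in 4 of the 96 scenarios, all with a mean fall of 10 and a change SD of 10. The third range spans nearly everything, so it shows that the size cannot be fixed from the documents.

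**The case against.** The strongest reply is that the two limits do different jobs. Exclusion 17 is an eligibility rule; the Appendix 2 limit is a descriptive flag, and Protocol 11.4 expressly leaves markedly abnormal criteria to the SAP. Other analytes differ in the same way. Ammonia is excluded at ≥2 × ULN but flagged at ≥1.5 × ULN. White cells are excluded at <3,000/µL but flagged below 0.85 × 4.5 = 3.825 × 10⁹/L at ages 6 to 17. This stands: the mismatch is not in itself a contradiction, and nothing in the documents shows that 20 ng/mL is an error. A milder flag is also more sensitive, which has value in a safety study stopped early for slow enrollment.

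It is also true that the protocol's key endpoint for this marker is change from baseline. SAP 7.5 reports that without restriction by baseline value, the listing in 7.10 includes every flagged child, and SAP section 7 plans no formal testing. A child going from 15 to 10 is therefore visible. What remains is that neither output gives a count by arm of children who newly fall below 12.

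A reader might infer more: that most counted cases are not deficient, that the table misses most new deficiencies, or that a treatment difference is hidden. The documents do not support these readings. The first holds in 92 of the 96 assumed scenarios but rests on assumed distributions; the second ranges from 7% to 97%; and the third overlooks the other outputs.

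Nor are all children at 12 to <20 certain to enrol. Exclusion 17 is an open-ended list, so an investigator may exclude some of them on judgement.

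**Conclusion.** The point holds as a limitation of one descriptive table. From the text alone, a child with a central baseline of 12 to <20 ng/mL cannot appear in the new-low incidence table after falling below 12, and a child who does appear need not be deficient on the protocol's limit. This assumes only that the absent-at-baseline condition is applied to the Appendix 2 flag on central values, as written.

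The number of children affected is unknown; the scenario ranges are illustrations. The individual values are not lost, because they remain in the change-from-baseline summaries and the listings. This is a worthwhile, inexpensive improvement for a listed bone marker, and it does not invalidate an analysis.

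**What to change.** Reconcile the SAP flag with the protocol limit by reporting both:

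- Keep the <20 ng/mL row in Appendix 2.
- Add a separate row for new values <12 ng/mL (<30 nmol/L), with the absent-at-baseline condition applied to that cut-off. A child who goes from 15 to 10 is then counted as new.
- Add a shift table by treatment group from baseline to post-baseline category: <12, 12 to <20 and ≥20 ng/mL.

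Keeping the <20 row avoids the loss of sensitivity that replacing it would bring.

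The cost is one extra row and one small table from data already collected; counts below 12 are likely to be small. One gap remains. A child admitted on a local result may have a central baseline already below 12, and so still cannot count as new at that cut-off. Such children should be shown in the <12 baseline category of the shift table.

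### SAP Appendix 2 sets markedly-low PTH limits inside or above the protocol's normal range, and its 1,25-dihydroxy-vitamin D conversion factor is about 3.3 times too large

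*SAP*

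**What the plan says.** SAP Appendix 2 extends its main chemistry table to four bone-related markers: "In addition, the MAL low and high for additional parameters will be as follows". For PTH, in pg/mL, the low limits are <40 (ages 2-7), <50 (8-10), <70 (11-12) and <100 (13-16). The matching high limits are >350, >490, >750 and >1100. For 1,25-dihydroxy-vitamin D the limits are <15 and >90 pg/mL. The conversion table follows: "The conversion factors for 25 Vitamin D, 1, 25 Vitamin D and PTH are listed below". It gives 0.4 for 25-hydroxy-vitamin D (nmol/L to ng/mL), 1.355 for 1,25-dihydroxy-vitamin D (pmol/L to pg/mL) and 9.434 for PTH.

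Protocol 4.2, criterion 17, states "Parathyroid hormone (normal reference range is 14.0 to 72.0 pg/mL", without an age split. For 25-hydroxy-vitamin D it gives a paired threshold: "level for clinically significant vitamin D deficiency is <12.0 ng/mL, conventional units [<30 nmol/L, SI units".

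SAP 7.10 makes the SAP's figures govern: "The reference ranges for labs from the SAP will be used, not the reference ranges provided from the Covance". It tabulates subjects with markedly abnormal values "that were not present at baseline will be provided", and it separately lists subjects with any markedly abnormal result.

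**The concern.** A markedly-abnormal limit should lie beyond the normal range. Appendix 2 does this for calcium (normal 2 to 2.6, flags at 1.7 and 3), sodium (135 to 148, flags at 127 and 158) and potassium (3.5 to 5, flags at 3.0 and 5.7). The PTH low limits do not, and no other SAP range puts this right, because Appendix 2 gives PTH no separate normal limits.

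The 1,25-dihydroxy-vitamin D factor is more than three times that of a molecule differing from it by one hydroxyl group.

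Both analytes are named markers of bone mineralisation among the key safety endpoints (Protocol 11.4; SAP 7.5). At stake is a safety table and listing that would mislabel normal values and leave clearly raised PTH unflagged.

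**Working it through.** **PTH.** Inputs: normal range 14.0 to 72.0 pg/mL (Protocol 4.2, criterion 17), so its width is 72 - 14 = 58; limits from SAP Appendix 2. Share of the normal range labelled markedly low = (low limit - 14)/58, capped at 1. High multiple = high limit/72.

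| Age | Low limit | Position | Share of normal range below it | High limit | Multiple of 72 |
|---|---|---|---|---|---|
| 2-7 | 40 | inside | 26/58 = 45% | 350 | 4.9 |
| 8-10 | 50 | inside | 36/58 = 62% | 490 | 6.8 |
| 11-12 | 70 | inside | 56/58 = 97% | 750 | 10.4 |
| 13-16 | 100 | above | 100% | 1,100 | 15.3 |

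These shares are widths of the range, not proportions of children. A proportion needs a distribution, which the documents do not give. If 14 to 72 is assumed to be the central 95% of a log-normal distribution, about 71%, 86%, 97% and 99.7% of healthy children fall below the four limits. That is illustration only; the finding does not need it.

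Effect under the SAP 7.10 counting rule:

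- At 13-16, any child with a normal baseline PTH is already markedly low, so an emergent fall cannot be counted.
- At younger ages, ordinary variation creates false events. A 5-year-old moving from 42 to 38 pg/mL (illustrative values, both normal) is counted.
- SAP section 7 takes age at each visit. A child steady at 45 pg/mL who turns 8 on study therefore becomes markedly low with no change in PTH.
- At every age, PTH several times the upper limit escapes the high flag.
- The listing has no baseline condition, so normal values appear in it at all ages.

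**1,25-dihydroxy-vitamin D factor.** The factor from nmol/L to ng/mL, or from pmol/L to pg/mL, is molar mass/1000.

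1. The 25-hydroxy factor reproduces from the protocol's pair: 12/30 = 0.400. This matches the SAP and implies about 400 g/mol.
2. The 1,25-dihydroxy form carries one more oxygen (about 16 g/mol). Assumption, not in the documents: molar mass about 416 g/mol, giving 0.400 + 0.016 = 0.416. The range is 0.400 (25-hydroxy factor unchanged) to 0.417.
3. The listed 1.355 would imply 1,355 g/mol. Inverting does not explain it: 1/0.416 = 2.40.
4. Ratio: 1.355/0.416 = 3.26, with range 1.355/0.417 = 3.25 to 1.355/0.400 = 3.39.
5. Where results arrive in pmol/L, the two limits act at 15/1.355 = 11.1 and 90/1.355 = 66.4 pmol/L. In true units these are 11.1 × 0.416 = 4.6 and 66.4 × 0.416 = 27.6 pg/mL. The share of the SAP's own 15 to 90 interval flagged high is then (90 - 27.6)/(90 - 15) = 83% of its width.

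**The case against.** The strongest reply concerns reach. SAP section 7 plans no formal testing. SAP 7.5 summarises observed PTH and its change from baseline without using these limits, and bone mineralisation is assessed mainly by DEXA, which is untouched. All laboratory data are listed, and Protocol 9.3 requires investigators to review laboratory reports and record clinically relevant changes as adverse events. All of this stands. The defect lies in a descriptive flag table and listing, and raised PTH would not vanish from the report; only its flag would.

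The second reply is that the conversion factor may never be used. The documents do not state the unit in which the laboratory reports 1,25-dihydroxy-vitamin D. If it is pg/mL, no flag is affected. This also stands, although supplying a pmol/L conversion suggests that conversion was expected.

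Two stronger readings are tempting:

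- A reader might infer that the PTH rows were pasted from the IGF-1 rows in another unit. Both rise with age, and the high-limit ratios are similar (350/50 = 7.0, 490/65 = 7.5, 750/100 = 7.5, 1100/140 = 7.9). But the first two age bands differ (2-8 and 9-10 for IGF-1, 2-7 and 8-10 for PTH), and the low-limit ratios run 6.7, 6.3, 4.7 and 5.0. The documents do not show where the numbers came from.
- A reader might infer that the whole emergent table is emptied. The baseline exclusion does that to the PTH-low count mainly at 13-16. In younger children the likelier distortion is false events.

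**Conclusion.** Both entries need correction. The PTH contradiction rests on the documents alone: three low limits inside 14.0 to 72.0 pg/mL, one above it, and high limits 4.9 to 15.3 times the upper end. The listing is wrong at all ages, and the emergent count is distorted in a direction that depends on age.

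The 1,25-dihydroxy-vitamin D factor is inconsistent with the SAP's own 0.4 and about 3.3 times too large (3.25 to 3.39), given the stated molar-mass assumption. Its consequences are conditional on results reported in pmol/L. In that case the flags act at about 4.6 and 27.6 pg/mL, and converted summaries, including changes from baseline, are inflated by the same multiple.

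The 25-hydroxy-vitamin D factor is right. The PTH observed and change-from-baseline summaries and the DEXA analyses are unaffected.

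**What to change.** - Reconcile the PTH markedly-abnormal limits with criterion 17 and the laboratory manual, so that both lie outside the normal range. Simply using 14 and 72 would not do: a value just under 14 would then count as markedly abnormal.
- Confirm the unit in which 1,25-dihydroxy-vitamin D is reported, and replace 1.355 with about 0.416.
- Re-run the markedly-abnormal table, the listing, and any 1,25-dihydroxy-vitamin D summaries that used the conversion.

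The cost is a short SAP correction, a query to the central laboratory and a re-run of those outputs. No new data are needed.
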